**May 5th, 2024**

# PROTOCOL

## *General Procedures*

Participants completed three phases: Listening Session #1, Earmold Fabrication, and a Listening Session #2. See **Figure 4.2**. The primary distinction among listeners was the material-type of earmold they received first. There are three material-types and thus three groups that participants could be initially assigned to. All participants received and were tested with each of the three material-type groups. Earmolds were connected to the same Unitron T-Stride M behind-the-ear hearing aid.

**Figure 4. 1** Participant-study flow chart for RCT study.

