### Earmold Fabrication Period

After completing Listening Session #01, ear impressions were digitally scanned and edited using commercially available 3D editing software. The physical ear canal impression was then sent to a third-party earmold manufacturer. Each participant was made three earmolds, for an overall total of 90 earmolds. For each individual, one earmold was created using a *third-party* manufacturer with the traditional service delivery pathway and two earmolds were created *in-house* with the novel service-delivery pathway using local 3D printers. The *third-party* earmold served as the control earmold. The *in-house* earmolds were made from two different material-types and served as the study earmolds. To control for style of earmolds, all earmolds were made in a skeleton style with a sound bore that accommodates size #13T tubing and a separate select-a-vent (SAV).

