### Listening Session #02

Once all earmolds were fabricated and received, participants were scheduled for Listening Session #02. This stage involved collecting objective acoustic measurements and subjective perceptual ratings while wearing each of the earmolds. A stock Unitron T-stride M behind-the-ear hearing aid was programmed to simulate a flat, mild, sensorineural hearing loss at

40 dB HL from octave frequencies between 250 to 8000Hz. The hearing aid was programmed and fit to NAL-NL2 targets for these threshold values. All advanced hearing aid programming and features were disabled. The same hearing aid was used across all participants. Participants underwent objective and subjective measures three times, once for the *third-party* control earmold and twice for each *in-house* study earmold. Each material-type condition was separated by a short 10 minute washout period, during which participants completed a self-assessment questionnaire.

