## ANALYSIS PLAN

The alpha level of statistical significance was set at .05 for all statistical analyses. The main statistical analysis included a one-way, within group, repeated measures analysis of variance (RM-ANOVA) to compare the effect of 3D printed material across outcome measures. Assumption testing for normality, outliers, and sphericity were utilized. Outliers were assessed on an individual basis, using Cook's D and a strict cutoff of 0.5. Sphericity was evaluated using Mauchly's test for Sphericity with a criteria of .05. If sphericity was violated, then both Geisser & Greenhouse and Huynh Feldt correction factors were used, with the latter being used when epsilon was greater than .075. Pairwise t-tests with Bonferroni correction were used for planned comparisons.

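### With three materials epsilon cannot fall below 0.50, so the .075 cut-off always selects Huynh-Feldt and the Greenhouse-Geisser correction can never be used (small numerical effect)

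*Combined protocol and SAP*

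**What the plan says.** The Analysis Plan section makes a one-way repeated measures ANOVA, with material as the within-subject factor, the main analysis for the outcome measures. Sphericity is tested with Mauchly's test at .05. On rejection the plan brings in two corrections: "If sphericity was violated, then both Geisser & Greenhouse and Huynh Feldt correction factors were used". The choice between them rests on the size of epsilon, Huynh-Feldt being the second one named: "with the latter being used when epsilon was greater than .075". That leaves Greenhouse-Geisser for epsilon at or below the cut-off. The plan does not say whether the epsilon compared with the cut-off is the Greenhouse-Geisser or the Huynh-Feldt estimate.

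The number of levels comes from General Procedures: "There are three material-types and thus three groups that participants could be initially assigned to", and "All participants received and were tested with each of the three material-type groups". The number of participants follows from Earmold Fabrication Period: "Each participant was made three earmolds, for an overall total of 90 earmolds".

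**The concern.** A rule that chooses between two corrections needs a cut-off inside the range that epsilon can take. For a factor with k levels that range runs from 1/(k-1) to 1. With k = 3 it starts at 0.50, far above .075, so the test on epsilon decides nothing.

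The plan then cannot do what it describes. Anyone applying it literally uses Huynh-Feldt every time, which is the less conservative of the two corrections at every epsilon above 0.50. If the analyst used some other cut-off, the plan misdescribes the analysis. Either way, a p-value close to .05 cannot be traced to a working rule.

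**Working it through.** **Inputs.** k = 3 materials (General Procedures). n = 90/3 = 30 participants (Earmold Fabrication Period). This agrees with the randomization list of three blocks of ten, 3 x 10 = 30. Alpha is .05 and Mauchly's criterion is .05 (Analysis Plan). The cut-off .075 is a stated rule, not a calculated figure, so there is nothing to reproduce. The question is whether it can ever separate the two corrections.

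**Step 1: bound on the Greenhouse-Geisser estimate.** Let a and b be the two eigenvalues of the contrast covariance matrix. Then e = (a + b)² / [2(a² + b²)]. Since ab ≥ 0, (a + b)² ≥ a² + b², so e ≥ 1/2. In terms of Mauchly's W, e = 1/(2 - W) with W between 0 and 1. The floor of 0.50 is 0.50/0.075 = 6.7 times the cut-off. For the floor 1/(k-1) to fall to .075, k would have to be at least 1/0.075 + 1 = 14.3, that is, 15 or more levels.

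**Step 2: bound on the Huynh-Feldt estimate.** h = [n(k-1)e - 2] / {(k-1)[n - 1 - (k-1)e]}, capped at 1. For k = 3, before the cap, h - e = 2(2e - 1)(e + 1) / [2(n - 1 - 2e)]. This is zero at e = 0.50 and positive above it. So h ≥ 0.50 as well, and it does not matter which estimate the plan means.

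**Step 3: where a correction applies.** At n = 30 Mauchly's test rejects when W < 0.05^(2/28) = 0.807, that is, when e < 1/(2 - 0.807) = 0.838. A correction is therefore used only for e between 0.50 and 0.838, and all of that range exceeds .075.

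**Step 4: how far the two corrections differ at n = 30.** Critical values are F on (2e, 58e) and (2h, 58h) degrees of freedom. The last column takes the F value that gives exactly p = .0500 under Huynh-Feldt and evaluates it under Greenhouse-Geisser.

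| e | h | h - e | F crit, Greenhouse-Geisser | F crit, Huynh-Feldt | Greenhouse-Geisser p |
|---|---|---|---|---|---|
| 0.50 | 0.500 | 0 | 4.183 | 4.183 | .0500 |
| 0.55 | 0.556 | 0.006 | 4.020 | 4.003 | .0505 |
| 0.60 | 0.611 | 0.011 | 3.878 | 3.847 | .0509 |
| 0.70 | 0.725 | 0.025 | 3.640 | 3.589 | .0518 |
| 0.75 | 0.782 | 0.032 | 3.539 | 3.480 | .0522 |
| 0.80 | 0.839 | 0.039 | 3.448 | 3.382 | .0526 |
| 0.838 | 0.883 | 0.046 | 3.384 | 3.314 | .0528 |

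**Step 5: simulation under the null.** Normal data, n = 30, 100,000 trials per row, Mauchly's test at .05. The rule as written is compared with an assumed cut-off of .75 on the Greenhouse-Geisser estimate.

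| True epsilon | Greenhouse-Geisser used, .075 | Greenhouse-Geisser used, .75 | Type I error, .075 | Type I error, .75 | Decisions that differ |
|---|---|---|---|---|---|
| 0.501 | 0 | 100% | 5.02% | 5.02% | 0.00% |
| 0.55 | 0 | 100% | 5.05% | 5.01% | 0.05% |
| 0.60 | 0 | 99.6% | 5.11% | 5.02% | 0.09% |
| 0.65 | 0 | 94.6% | 5.09% | 5.00% | 0.09% |
| 0.70 | 0 | 79.4% | 5.23% | 5.11% | 0.12% |
| 0.75 | 0 | 56.3% | 5.08% | 5.00% | 0.08% |
| 0.85 | 0 | 18.0% | 5.06% | 5.03% | 0.02% |
| 1.00 | 0 | 0.3% | 5.03% | 5.03% | 0.00% |

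The smallest estimate seen was 0.5002. Runs of 200,000 trials gave the same picture, with at most 0.13% of decisions differing.

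**Step 6: sensitivity to the assumed cut-off.** At true epsilon 0.70, Greenhouse-Geisser would be used in about 25%, 56%, 79% and 92% of trials for cut-offs of .65, .70, .75 and .80. At 0.775 the figures are about 5%, 21%, 45% and 68%. Decisions differed from the rule as written in no more than about 0.15% of null trials at any of these cut-offs.

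**The case against.** The best case for leaving this alone is that nothing of substance turns on it. Always using Huynh-Feldt after Mauchly's test rejects is a usable procedure with close to nominal error, and the number is probably a typing slip. That stands, and it is why the point is minor. It does not make the written rule workable.

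The figures for how often Greenhouse-Geisser would be used depend on a cut-off that the documents do not give. That also stands: they describe the assumed value, not the plan. The unreachable branch needs no such assumption.

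The count of three measurements can be questioned. Listening Session #02 says "Participants underwent objective and subjective measures three times", but the same sentence goes on to describe the in-house sets in words that could be read as two per in-house earmold, or five sets in all. Five levels would give a floor of 1/(5-1) = 0.25, still above .075. General Procedures is the clearer source for three levels.

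Finally, which epsilon estimate is meant makes no difference to the rule as written. It matters only once a workable cut-off is in place, so it is a clarification and not a second defect.

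**Conclusion.** The concern holds. With three materials both epsilon estimates are at least 0.50, so the .075 condition is always met when a correction is applied, and Greenhouse-Geisser cannot be reached. This part rests only on the three-level factor. Nothing else in the documents supplies a different cut-off.

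The consequence is small. At n = 30, against an assumed cut-off of .75, type I error rises by at most about 0.12 percentage points (5.23% against 5.11%), and a reported result could change only if its p-value is very close to .05. The two corrections coincide at e = 0.50 and move apart as e rises. At or below .75 the gap is at most 0.032. It reaches 0.046 near 0.838, but a .75 cut-off would use Huynh-Feldt there anyway. These sizes assume normal data and 30 complete participants. A misplaced decimal point is a plausible explanation but cannot be shown from the documents.

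**What to change.** - Replace .075 with a cut-off that lies within the range epsilon can take when Mauchly's test rejects (0.50 to 0.838 at n = 30). The value .75 is likely, but the sponsor must confirm it.
- State that the cut-off is compared with the Greenhouse-Geisser estimate. With .75 and n = 30 this matters for estimates between 0.722 and 0.75, because Huynh-Feldt already reaches .75 at e = 45.5/63 = 0.722, and the two estimates then fall on opposite sides.
- If the analysis has been run, report which cut-off and which correction were used for each outcome where Mauchly's test rejected, and correct any affected p-values.

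The cost is one number and one clause, plus that check if results exist. With a .75 cut-off, p-values for outcomes at or below it become slightly larger; a .050 moves by about .002 at most.

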## Randomization

Each participant was made three earmolds for a single ear. The main difference between participants was the material-type of earmold that they received first. All participants were eventually fit with and underwent testing with each earmold material-type. Participants were randomly assigned to one of three arms, using a 1:1 allocation ratio, each with a different initial material type. The three material-type groups included a control group (EMCTRL) made by a professional manufacturer, and two in-house study groups that were 3D printed using Resin (EMRES) and PLA (EMPLA). See **Figure 4.3**. Randomization was completed *a priori* via a list generated by a custom Microsoft Excel script. This script randomly sequenced three blocks of ten numbers equally containing values from 1 to 3. Once participants were deemed eligible, they were automatically assigned the next value on the randomized list, from 1 to 3, indicating which arm of the study they were allocated to.

**Figure 4.2** Workflow study diagram across material-type groups

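### Holm's step-down method could replace Bonferroni for the pairwise t-tests: same familywise control at .05, no rejection lost, modestly more power

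*Combined protocol and SAP*

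**What the plan says.** The Analysis Plan section compares the materials on each outcome with a one-way repeated measures ANOVA, and then: "Pairwise t-tests with Bonferroni correction were used for planned comparisons". On the error rate it says: "The alpha level of statistical significance was set at .05 for all statistical analyses". It names no stepwise procedure. It does not state how many comparisons form the family, or whether the ANOVA must be significant before the t-tests are read. It plans no simultaneous confidence intervals.

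The comparisons are within person. General Procedures says: "All participants received and were tested with each of the three material-type groups". Randomization repeats this: "All participants were eventually fit with and underwent testing with each earmold material-type". The sample size follows from Earmold Fabrication Period: "Each participant was made three earmolds, for an overall total of 90 earmolds".

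**The concern.** Single-step Bonferroni holds every comparison to the strictest threshold, even after one or two differences have been established. Holm relaxes the threshold after each rejection and still protects the familywise error rate. The study sets two in-house materials against a third-party control, so a second real difference is plausible, and that is where Bonferroni gives power away. With 30 participants and no power calculation in the documents, Bonferroni is somewhat more likely to miss a second or third real difference. The first difference is tested identically under both methods.

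**Working it through.** **Inputs**

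- Familywise level .05 (Analysis Plan).
- Three materials, all worn by every participant (General Procedures, Randomization). *Pairwise* is read as m = 3 paired comparisons per outcome. The documents do not state m, so m = 2 (each in-house mold against control) is shown as well.
- n = 90 earmolds / 3 per participant = 30. The randomization list agrees: 3 blocks × 10 = 30.
- Assumed, because the documents give neither effect size nor SD: normal data, equal correlation between conditions, and effects in units of the SD of the paired difference.

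**Thresholds**

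- Bonferroni: .05/3 = .0167 for each test. The total is 3 × .0167 = .05, which matches the stated alpha.
- Holm: .05/(m − i + 1) for the i-th smallest p-value, stopping at the first non-rejection. This gives .05/3 = .0167, .05/2 = .025 and .05/1 = .05.
- Observed mean difference needed at n = 30 (df 29): .464 SD at .0167, .432 SD at .025 and .373 SD at .05.

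**Why Holm loses nothing**

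Every Holm threshold is at least .0167, so any p-value at or below .0167 is rejected by both methods. For error control, suppose m₀ null hypotheses are true. When Holm first rejects a true one, at least m₀ hypotheses are still in play, so that p-value is at most .05/m₀. By the Bonferroni inequality the chance of this is at most m₀ × .05/m₀ = .05. The argument holds under any dependence among the tests, so it needs neither sphericity nor a significant ANOVA.

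**Simulation** (200,000 trials per case, n = 30, two-sided paired t-tests, m = 3, no ANOVA gate)

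Both in-house molds differ from control by d; each cell is Bonferroni / Holm:

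| | d = 0.3 | d = 0.5 | d = 0.7 |
|---|---|---|---|
| Power per true comparison | .203 / .218 | .583 / .618 | .894 / .917 |
| Both differences detected | .0855 / .1152 | .4156 / .4865 | .8217 / .8681 |
| At least one rejection | .325 / .325 | .751 / .751 | .966 / .966 |
| False resin-versus-PLA claim | .0164 / .0227 | .0169 / .0316 | .0169 / .0434 |
| Trials with a Holm-only rejection | .0364 | .0832 | .0695 |

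- Bonferroni rejections missed by Holm: 0.
- No true differences: familywise error is .0445 for both methods.
- Only one in-house mold differs, by 0.5: power for its comparison with control goes from .583 to .618.
- Molds differ from control by 0.7 and 0.35: power for the smaller difference goes from .284 to .372, a gain of .088.
- Sample-size equivalent at d = 0.5: Bonferroni needs n = 32 to reach .619, against .618 for Holm at n = 30.
- Sphericity violated (epsilon .9 and .8), d = 0.5: power per comparison goes from .583 to .621 and from .582 to .615. With no true differences, familywise error is .043 and .042 for both methods.

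**If only two comparisons were meant (m = 2)**

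Bonferroni uses .025 twice; Holm uses .025 and then .05. With both molds differing by 0.5, power per comparison goes from .647 to .707 and power for both from .489 to .610. If only one mold differs, there is almost no gain (.647 to .649).

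**The case against.** The best counter-argument is that nothing in the plan is wrong. Bonferroni is valid, the per-comparison gain is only .015, .035 and .023 at 0.3, 0.5 and 0.7 SD, and the chance of any finding is unchanged. That is true, and it is why this is an inexpensive improvement and not a defect.

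The plan is written in the past tense. If the analysis has been run, replacing the sentence would misdescribe what was done. This stands as a limit: Holm could then only be added as a labelled post hoc analysis.

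Part of the gain is paid for in false claims. At 0.7 SD, the false resin-versus-PLA rate rises by .0434 − .0169 = .0265, against .917 − .894 = .023 in power per comparison. This also stands, but the rate remains within the .05 that the plan accepts. At 0.3 and 0.5 the power gained for the two true comparisons together exceeds the added false claims.

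Holm is not the most powerful choice either. With all pairs among three means, one false null leaves at most one true null among the rest, so Shaffer's thresholds of .0167, .05 and .05 are also valid. At 0.5 SD they raise power for both differences to .587, against .486 with Holm in the same simulation. That is a legitimate alternative, but it does not favor Bonferroni. Holm is simple and works whether two or three comparisons are intended.

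Finally, the ANOVA may have been meant as a gate, which the plan does not say. At 0.5 SD a gate lowers Bonferroni's chance of at least one rejection only from .750 to .737.

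**Conclusion.** The point holds as an efficiency improvement. Holm's error control and its retention of every Bonferroni rejection follow from the method and need no assumption about the data beyond valid individual p-values. The size of the gain does rest on assumptions: 30 participants, normal data, three comparisons and illustrative effects. Under these, with both molds differing equally from control, power to detect both rises by about .03, .07 and .05 at 0.3, 0.5 and 0.7 SD. The chance of at least one finding does not change. The benefit for this particular trial is unknown, because the documents give no effect size.

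**What to change.** Replace the sentence on pairwise tests with:

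> Within each outcome, the three pairwise t-tests were adjusted by Holm's step-down method at a familywise level of .05. Holm-adjusted p-values are reported.

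If only the two comparisons with control are intended, say two instead of three.

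**Cost.** One sentence and no new data. Two consequences should be stated:

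- Holm has no simple matching simultaneous intervals. If Bonferroni intervals are shown, they will include zero for any comparison that only Holm rejects (3.6%, 8.3% and 7.0% of simulated trials at 0.3, 0.5 and 0.7 SD). The report should say that the intervals are wider than the test implies.
- Holm within each outcome, like Bonferroni, gives no control across outcomes. The available text names no primary outcome (part of the document was removed before review), so this is noted only as a limit.

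If results have already been seen, leave the Bonferroni analysis in place as the planned one and add Holm labelled as post hoc.
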